2.1 Data analysis general information

The statistical analysis will be performed by Novartis internal statisticians and programmers.

Unless otherwise stated, summary tables/listings/figures will be presented by treatment group in the respective analysis set. Tables showing only baseline data will also include a total column.

Categorical data will be summarized as frequencies and percentages. Percentages will be calculated as below:

- For population level summaries (like Demographic, AEs, Medical history...etc.), percentages will be calculated using number of participants in each reporting group as the denominator.
- For by visit summaries, percentages will be calculated using the number of participants in the analysis set with an assessment at the specified visit as the denominator.
- For specific event based summaries, the denominator will only include the subset of the analysis population of participants at risk at a specific point in time (Kaplan-Meier approach).

Continuous data will be summarized by presenting the number of non-missing observations, mean, standard deviation (SD), median, minimum and maximum, both for raw (absolute) values and for changes from baseline. Summary tables will be presented wherever applicable by visit if not otherwise specified.

Specified parameters of interest will be listed by treatment group, records will be ordered by country/center/participant and time of assessment.

General information on treatment group labels, decimal places and other output related information will be specified in the specification document for tables, figures and listing (TFLs) shells accompanying this analysis plan.

Statistical analysis will be performed using SAS[®] statistical software (SAS Institute, Cary, NC, USA.) version 9.4 or higher.

2.1.1 General definitions

Study Drug

Study drug refers to CNP520 50 mg, CNP520 15 mg, or placebo.

Date of First Study Drug Administration (Day 1)

Day 1 is defined as the first day of randomized study drug administration. All other days will be labelled relative to Day 1. For event dates on or after Day 1, study day for an event date is calculated as (event date – first dose date + 1) which could be Day 2, Day 3 etc. For event dates before Day 1, study day for an event date is calculated as (event date – first dose date), which could be Day -1, Day -2, etc., referring to one day, two days, etc., before Day 1, respectively. Thus, Day -1 is the day preceding Day 1. Day 0 is not defined.

Date of Last Study Drug Administration

The date of last study drug administration is the day of intake of the last dose of study drug.

Baseline

A baseline value refers to the last (most recent) evaluable measurement prior to Day 1. Typically, baseline values will be the values obtained on the day of randomization. If the Baseline visit is missing or the assessment was not done at Baseline, the last assessment of an earlier visit

(scheduled or unscheduled) which is closest to the Baseline visit will be used as Baseline value. In case an assessment is repeated at a later visit during the screening epoch, the latest one will be used as Baseline value.

Note: Assessments at the day of randomization are assumed to have been taken as per protocol, i.e. if the assessment should be performed before dosing, the assessment will be treated as pre-dose as per protocol. Practically, i.e. that the time part of the date/time entry (when collected) will be ignored. Exception: In case there is a protocol deviation or a comment that specifically indicates that the assessment has been taken post-dose, the assessment will not be handled as pre-dose.

Post-baseline

For safety and efficacy evaluations all assessments after Day 1 are defined as post-baseline assessments.

Roll-over participants

Participants from API015A2201J study (Generation study 1; GS1) may roll over to be enrolled into CNP520A2202J study (Generation study 2; GS2). These participants have been genotyped and disclosed in GS1.

Roll-over participants in GS2 have signed the GS2 Informed Consent Form (ICF/ICF#B), and GS2 inclusion/exclusion criteria were verified. The participant received a new subject identifier in GS2. Some of the screening assessments for these participants will be repeated in GS2, and for some assessments, data obtained in GS1 will be re-entered. More details on data collection for roll-over participants is outlined in [Appendix 5.7](#).

Note: For roll-over participants, data collected in GS1 and skipped in GS2 are expected to be mapped (re-entered) from the GS1 to the GS2 database. Hence, there is no programming effort expected to map the data from GS1 to GS2.

Re-screened participants

Participants who screen-failed due to a temporary condition (e.g. physical, concomitant medications, etc.) or due to administrative reasons may be re-screened after resolution. The participant will receive a new subject identifier at re-screening. The latest screening assessment will be considered for reporting at screening visit. Assessments (like genotype, volumetric MRI, etc.) that are not repeated, will be carried over. This is based on mapping the old subject identifier to the new subject identifier.

In general, all data collected under the old subject identifier is kept after mapping to the new subject identifier. This comprises for instance AEs, vital signs, ECG, and laboratory data. In case of missing values under the new subject identifier, the latest available value from the old subject identifier will be used. In study GS2, the earliest consent date is kept, if the subject is re-screened

Prior and Concomitant Medication

Prior medication will be defined as any medication taken prior to the first dose of the study drug, irrespective of whether the medication continued into the treatment period.

Any medication administered at least once between Day 1 and end of the study is defined as concomitant medication.

Visit Windows

In general, by-visit analyses will include data from scheduled as well as un-scheduled visits using visit windows for scheduled visits except for TEC/PPW and EoS. In general, the lower and upper bound of a visit window will be defined as the midpoint between scheduled visits. The visit window rules for efficacy and safety parameters are defined in [Appendix 5.8](#).

For efficacy parameters: In case of competing assessments within a visit window, the assessment value closest to the scheduled visit day will be used. In case of equal distances, the earliest assessment value will be used. Visit window will not be applicable for TEC and EoS.

For safety parameters: In case of competing assessments within a visit window, the worst assessment value within the visit window will be used. This rule also applies for worsening in cognition as a safety measure.

Listings will include all assessments, sorted by date of assessment, flagging unscheduled visits. The listings will include analysis windows and corresponding flags to indicate the assessment's inclusion in the analysis.

Treatment Epoch Completion (TEC) and End of Study (EoS) and other points in time of interest

TEC is the end of treatment phase visit (i.e., visit 299) that will be completed for all participants after discontinuation of treatment. The same visit will also be completed in case of PPW. PPW is the premature study withdrawal.

EoS is a Follow-up visit scheduled after TEC/PPW, per urgent safety measure (USM) on 11-Jul-2019, and its follow-up letter dated 12-Dec-2019, Modified EoS visits can be scheduled anytime after receipt of this notification but no later than 15-Mar-2020. (i.e. the requirement from 11 July 2019 USM for the 6 month timeframe between modified TEC and mEoS visits is no longer required.).

Participants who were attending study visits (i.e., continuing in the study) but already off-treatment at time of USM were to come for EoS straight (no TEC required).

An assessment will be on treatment if it is before or at last day on study drug + 31 days. The last assessment before or at last day on study drug + 31 days will be referred to as "last on treatment" assessment. The last assessment after last day on study drug + 31 days will be referred to as "last off treatment" assessment. For deriving "last on treatment" or "last off treatment", last assessment date of RBANS will be used. That means, to derive the last on treatment and last off treatment for all the parameters, regardless of their actual assessment

dates, RBANS last assessment date will be used as reference date. Note: the “last on treatment” and “last off treatment” flag will be created for each participant at visit level (not at the individual assessment level). If there is missing RBANS assessment at the specific visit, then date of the first day corresponding to that visit (i.e. non-missing assessment of that parameter under consideration) will be used to derive the “last on/off treatment” assessment.

Note: On treatment is a period from first dose to last dose + 31 days.

For example:

1. If a participant has the last dose on 13-Jul-2019, then “on treatment” period would span from first dose to 13-Jul-2019 + 31 days.
2. If a participant has the last dose on 09-Apr-2019, then “on treatment” period would span from first dose to 09-Apr-2019 + 31 days.

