Due to the early termination of the clinical trial, most of the primary, key secondary and the secondary objectives cannot be addressed with the data collected until termination. The originally planned inferential statistical analyses comparing efficacy readouts at Month 60 across treatment groups will not be conducted, but data collected on primary and secondary variables will be reported descriptively.

All the efficacy and biomarker endpoints except from events and TTE itself will be summarized using descriptive statistics by treatment groups (including active total, i.e., CNP520 Total) as follows

- Raw values by visit including the “last on treatment”, “last off treatment”, TEC and the EoS follow-up visit
- Change from baseline by visit including “last on treatment”, “last off treatment”, TEC and EoS
- Change from “last on treatment” visit to TEC, change from “last on treatment” to “last off treatment”, change from “last on treatment” visit to EoS and change from TEC to EoS

Note: Time of “last on treatment” and “last off treatment” will be discussed in CSR statistical Appendix 16.1.9, specifications will be described in the TFL shells document in Section 16.1.9.

All the safety data will be summarized using descriptive statistics by treatment groups (including active total, i.e., CNP520 Total).

Analysis of genetic disclosure follow-up and amyloid disclosure follow-up will be summarized using descriptive statistics by genotype and/or amyloid status groups as described in [Section 2.3.2](#).

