2.8.1 Adverse events (AEs)

Treatment-emergent AEs (TEAEs) are events that either started after the first dose of study drug or events present prior to the start of study drug but increased in severity since the first dose. Adverse events reported within 31 days (5 half-lives) from study drug discontinuation date (i.e., last dose date) will be considered as TEAE. AEs reported more than 31 days after study drug discontinuation will not be considered treatment emergent (non-TEAE).

TEAEs and non-TEAEs will be summarized separately on the SAF.

Tables

TEAEs, SAEs, deaths and non-TEAEs will be summarized as follows

- TEAEs regardless of relationship to study drug by SOC, PT and maximum severity
- non-TEAEs, regardless of relationship to study drug by SOC and PT
- TEAEs causing study drug discontinuation by SOC, PT and maximum severity
- TEAEs related to study drug by SOC, PT and maximum severity
- TE-SAEs regardless of relationship to study drug by SOC and PT and maximum severity

Note: For missing information on AE relationship to study drug, the most conservative approach will be considered: If information on relationship of the AE to study drug is missing, the AE will be considered as related to study drug for reporting TEAEs.

The above summaries are generally without exposure adjustment, except from TEAEs by SOC and PT: this summary will be presented with exposure adjustment. The exposure-adjusted incidence rate of adverse events is defined as the number of participants with the adverse event divided by total participant years at risk in the treatment group. The time at risk for each participant will differ for each adverse event. For participants with events, only the time until the first event contributes to the total participant years at risk. For participants who do not experience the event, the time at risk will be calculated using the duration of exposure as defined in [Section 2.4.1](#). The exposure-adjusted incident rate will be summarized per 100 participant years. For participants with multiple occurrences of the same event, the event will be counted only once per participant.

Adverse events will be reported according to the latest MedDRA dictionary version available at the time of database lock.

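### The change from last on treatment to TEC is zero by construction when visit 299 falls within 31 days of the last dose and is itself the last on-treatment visit

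*SAP*

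**What the plan says.** - **Window.** SAP 2.1.1: "An assessment will be on treatment if it is before or at last day on study drug + 31 days". The last assessment inside that window is *last on treatment*; the last one after it is *last off treatment*.
- **Level of the flag.** The "flag will be created for each participant at visit level (not at the individual assessment level)". A visit is dated by its RBANS. "If there is missing RBANS assessment at the specific visit, then date of the first day corresponding to that visit" is used instead.
- **TEC.** SAP 2.1.1 defines TEC as visit 299, completed after treatment is discontinued and also used for PPW. No minimum gap from the last dose is required. The only exception made for TEC in the timing rules is that visit windows do not apply to it.
- **Contrast.** SAP Section 2 lists several within-participant changes for the efficacy and biomarker endpoints other than events and TTE. The bullet containing "visit to TEC, change from" plans the change from *last on treatment* to TEC.
- **Summary statistics.** SAP 2.1: "Continuous data will be summarized by presenting the number of non-missing observations, mean, standard deviation (SD), median, minimum and maximum".
- **Deferred detail.** A note in SAP Section 2 says the time of these two visits "will be discussed in CSR statistical Appendix 16.1.9, specifications will be described in the TFL shells document in Section 16.1.9".

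**The concern.** The contrast presumes two different visits, but the definitions allow them to be one. When they coincide, the SAP does not make the pair not evaluable, so it enters the table as a change of 0. That zero says nothing about what happens after stopping.

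Inferential Month 60 analyses were dropped, so descriptive summaries are what the report will contain. Reversibility after stopping is a stated topic of SAP 2.5.1. Structural zeros pull the mean of this contrast towards no change, add pairs with no information to n, and can force the median to 0.

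**Working it through.** **1. The window.** SAP 2.8.1 equates 31 days with 5 half-lives. Protocol 1.1 gives a terminal half-life of about 150 hours: 5 × 150 / 24 = 31.25 days, so the figure is reproduced.

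**2. The rule applied literally.** Take the SAP's own example of a last dose on 13-Jul-2019, so that on treatment runs to 13-Aug-2019. Give a made-up participant an earlier visit with a change from baseline of −4 and a TEC value of −1.

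| TEC, days after last dose | *Last on treatment* visit | Change to TEC |
|---|---|---|
| 1, 7, 14, 31 | visit 299 | −1 − (−1) = 0 |
| 32, 45, 60, 91 | earlier visit | −1 − (−4) = +3 |

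**3. Can visit 299 fall in the window?** Three routes allow it; the documents give no frequency for any of them.
- Amendment 03 records an immediate stop in July 2019. Protocol Table 6-1, footnote 42, places the modified TEC at the next scheduled visit, and Protocol 3.1 has visits every three months. Some next visits would fall soon after the stop.
- Protocol 5.6.3 asks for the PPW assessments before withdrawal. A participant still on drug would have visit 299 within days of the last dose.
- SAP 5.1.1 sets a missing treatment end date to the TEC date, a gap of 0 days, with details left to the programming specifications.

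Protocol 5.5.4, with the last dose the day before TEC, describes the superseded completion path and is not relied on.

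**4. Who gives no zero.** Parameters not measured at visit 299 give a missing value. PET was cancelled at the modified TEC (footnote 42), and MRI, blood biomarkers and lumbar puncture are conditional at PPW/TEC (footnote 37). Participants "already off-treatment at time of USM were to come for EoS straight (no TEC required)" give no pair.

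**5. Size, under stated assumptions.** Let p be the share of pairs that coincide.
- Mean = p × 0 + (1 − p) × mean of distinct pairs, so the scaling factor is 1 − p.
- n is overstated by 1/(1 − p).
- The median is 0 unless more than 0.5/(1 − p) of distinct pairs share a sign.

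The base case assumes gaps uniform over 0 to 91 days (three months). The variants use the ±4-week visit window in Protocol Section 6.

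| Assumed gap | p | Mean factor | n overstated | Same-sign share needed for a non-zero median |
|---|---|---|---|---|
| Uniform 0–91 days | 31/91 = 0.34 | 0.66 | 1.52 | 0.76 |
| Uniform 0–119 days (91 + 28) | 31/119 = 0.26 | 0.74 | 1.35 | 0.68 |
| Every visit 28 days late | (31 − 28)/91 = 0.03 | 0.97 | 1.03 | 0.52 |
| Every visit 28 days early | (31 + 28)/91 = 0.65 | 0.35 | 2.84 | not attainable; median always 0 |

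The last two rows are bounds, not expected cases.

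**6. What the documents say about actual gaps.** Amendment 03 describes post-treatment data from visits 1 to 8 weeks after wash-out. If wash-out means the 31 days, that is 31 + 7 = 38 to 31 + 56 = 87 days after the last dose. Some post-treatment visits therefore lay outside the window, but this does not give the share inside it.

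**The case against.** The strongest reply is that little depends on this contrast. The same part of SAP Section 2 also plans the change from *last on treatment* to *last off treatment*. That contrast is split by date, has no zeros of this kind, and answers the wash-out question better. TEC, *last on treatment* and *last off treatment* are each also summarised against baseline, and the SAP 2.5.1 effect sizes use those baseline changes. All of this is correct and keeps the point minor.

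The TFL shells, which are not available here, might suppress coincident pairs. That cannot be excluded. But the note in Section 2 concerns the timing of the visits, and the SAP's revision history adds only summaries of their distribution. Neither changes the derivation.

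The percentages rest on an assumed gap distribution. This stands. The uniform model describes only participants on drug at the July 2019 stop who came to their next scheduled visit, not PPW participants. A range of 3% to 65% amounts to saying that the share is unknown. The imputation route may also be rare for the July 2019 stops, because sites were told to document the last dose.

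Finally, a later visit still within 31 days would take the flag from visit 299. Footnote 43 of Protocol Table 6-1 allows the follow-up visit at any time within 12 weeks, so this is possible. It is unlikely to matter for cognition, because Amendment 03 no longer required cognitive testing at that visit.

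**Conclusion.** The concern holds and is minor. The mechanism follows directly from the SAP: a visit-level flag set by date, visit 299 not excluded, and a planned contrast from that flag to visit 299. It operates when visit 299 falls by last dose + 31 days, no later visit does, and the parameter was measured there. Confidence in the mechanism is high; how many participants it affects is not known. The 34% illustration (mean scaled to 0.66, n overstated 1.52-fold) depends wholly on a uniform 0 to 91 day gap among those stopped in July 2019. Only this one descriptive contrast is affected.

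**What to change.** In SAP Section 2 or 2.1.1, for the *last on treatment* to TEC contrast only, set the change to not evaluable (missing) when the *last on treatment* visit is TEC/PPW. In a footnote, report by arm how many participants this removes and how many last-dose dates were imputed as the TEC date under SAP 5.1.1. Keep the 31-day definition everywhere else.

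If a change from the last visit before TEC to TEC is also wanted, show it as a separately labelled contrast. For an in-window TEC it compares two visits that the SAP classes as on treatment, so it should not be read as change after wash-out.

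The cost is one derivation flag and a footnote. The contrast will have a smaller n, but only pairs that carry no information are lost.

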2.2 Analysis sets

The following analysis sets will be used.

The **Randomized analysis set (RAS)** will consist of all participants who received a randomization number, regardless of receiving study medication.

The **Safety analysis set (SAF)** will consist of all participants who received study medication.

Note: The above SAF definition is different from the protocol defined SAF definition which restricts to include only those participants in SAF if they have had at least one safety assessment after first dose administration.

The **modified SAF (mSAF)** will consist of all participants of the SAF with at least 3 months exposure duration.

All efficacy analyses (except worsening in cognition and reversibility) and safety analyses will be conducted on the SAF.

In addition, the following sets of participants will be used to understand the composition of analysis sets and disposition of participants.

The **Screened set** will consist of all participants completing any Screening visit. This set should comprise all participants who underwent any screening assessment.

2.2.1 Group for specific analysis

Analysis of worsening in cognition and assessing reversibility of worsening in cognition will be performed on the mSAF.

2.3 Patient disposition, demographics and other baseline characteristics

Summary tables for demographic variables and other baseline characteristics as well as relevant medical history will include an active total (pooled across active treatment arms) and a total column in addition to the treatment arms.

The impact of genetic and amyloid disclosure for the participants assessed for genetic disclosure and amyloid disclosure during the screening period will also be reported by genotype groups.

2.3.1 Patient disposition

The number and percentage of participants in each analysis set described above will be presented including all participants that started screening. Primary reason for screen failure will be summarized for all participants.

Participant disposition will be summarized for the RAS showing the flow of participants through the treatment epoch and completing the End of Study disposition page. The disposition summary will show the number and proportion of participants who discontinued treatment epoch and End of Study status along with the reason for discontinuation. The number and proportion of participants with missing End of Study assessment will also be reported. The primary reasons for premature discontinuation of study treatment will also be summarized. Listings will be provided showing the primary reason for premature discontinuation of study and of study treatment.

All the important protocol deviations (PDs) reported during the study will be summarized in the following five categories:

- Selection criteria not met
- Participant not withdrawn as per protocol
- Treatment deviation
- Prohibited concomitant medication
- Other deviations (important deviations that do not fall in the above four categories)

Important PDs are defined as subset of PDs that may significantly impact a subject's rights, safety, and well being or the completeness, accuracy, and/or reliability of the study data. The PD codes to identify the above categories are listed in [Table 5-4](#) in the Appendix.

